## C.2.c.5. Phase 1: Baseline and Medication Trial

- **a. Initial Study Visit.** Participants will be trained to use CREMA and the one-week naturalistic baseline data collection period will begin following screening procedures. If it is determined that patient is ineligible based on labwork, they will be excluded and baseline procedures will end.
- **b.** Baseline Assessment (Study days 1-7). Throughout this study period, participants will come to the clinic for UDS collection. To facilitate opioid abstinence during the baseline period, we will use a standard contingency-management procedure. Participants will earn payments of \$10 for the first negative UDS and \$20 for the second. Two consecutive UDSs during the baseline week must be negative for illicit opioids in order for the subject to enter the medication treatment part of the trial. During the baseline assessment period, participants will be asked to use CREMA (described below). Subjects may have up to 10 days to provide the negative UDSs.
- c. CREMA Assessment. Cue Reactivity Ecological Momentary Assessment (CREMA; Warthen & Tiffany, 2009; Wray, Godleski, & Tiffany, 2011; Wray et al., 2015) can collect subjective ratings of stress, craying, etc., either without provocation or using photos from the International Affective Picture System (IAPS; Lang, Bradley, & Cuthbert, 2008) presented on a mobile electronic device (iPhone). If an individual does not have an iPhone or does not wish to use his/her own for the study, a phone will be provided. Participants will be instructed to keep their phone with them at all times. Participants will complete a daily survey about substance use and stressful life events over the previous 24 hours. Auditory alarms will alert participants to complete one randomly scheduled session per day to rate stress, craving and mood. This visual analog scale is anchored with adjectival modifiers ("not at all, mildly, moderately, and extremely"). The scale includes items assessing anxiety, stress, irritability, and craving. Participants will also be alerted to daily random CREMA sessions including IAPS pictures; session will randomly include neutral IAPS pictures or stressful IAPS pictures (described below). Iindividuals be presented one of two types of picture cues that differ based on content: stress-related (i.e., a child in distress) or neutral (i.e., sunglasses). Each picture will appear only once during the study. Participants will be instructed to look at the photo carefully for 10 seconds. An alarm will sound at the end of the trial, and participants will complete a post-cue rating scale assessment, ratings of how carefully they looked at the photographs and their distraction level. Using this strategy, we can assess ambient emotional state and craving as well as "evoked" response to stressful cues. To encourage CREMA session completions, participants will be compensated \$10.00 for each day they complete all sessions. Previous studies employing this incentive strategy have reported 85-90% completion rates (Gass et al., 2011; Warthen et al., 2009), including in our previous SCOR work (Wray et al., 2015).
- d. Lofexidine/Placebo Titration Procedures (Days 8-17). After two consecutive negative drugs screens have been obtained, participants will be randomly assigned to study medication (lofexidine or matching placebo). For the Shoreline site, medication will be dispensed by IDS and delivered to MUSC staff at that site. At the randomization visit, females will provide saliva samples for estradiol and progesterone testing. Trained study personnel will evaluate heart rate, orthostatic blood pressure, and pre-syncope and syncope signs and symptoms prior to the initiation of Lofexidine. Lofexidine will not be dispensed if the participant is found to have

one of the following on physical exam: 1) clinically significant bradycardia as determined by study physician; 2) orthostatic hypotension defined as a systolic blood pressure decrease of at least 20mm Hg or a diastolic blood pressure decrease of at least 10mm Hg within three minutes of standing; 3) participant endorsement of presyncope symptoms such as lightheadedness, muscular weakness, blurred vision, or feeling faint during the evaluation of orthostatic blood pressure; or 4) syncope (fainting) during the evaluation of orthostatic blood pressure. Participants with bradycardia, orthostatic hypotension, pre-syncope or syncope would be terminated from the study and study staff will facilitate appropriate follow-up medical care. To minimize risks of hypotension, lofexidine will be titrated over a 10-day period with 0.36 mg QDfor days 1 and 2; 0.36 mg BID for days 3 and 4; 0.36 mg TID for days 5 and 6; 0.36 mg BID and 0.72 QD days 7 and 8; 0.37 QD and 0.72 BID for days 9 and 10, and 0.72 mg TID on day 11 and throughout the rest of the study (see **Table 2**). This is the dose recommended by the regulatory agencies in England and the titration schedule is consistent with lofexidine titration in 8 published studies (Gish et al., 2010).

Table 2

| Days                                      | AM Dose (mg) | PM Dose (mg) | QHS Dose (mg |
|---|--------------|--------------|--------------|
| Days 1 and 2 (Study days 8 and 9)         |              |              | 0.36         |
| Days 3 and 4
(Study days 10 and
11) | 0.36         |              | 0.36         |
| Days 5 and 6 (Study days 12 and 13)       | 0.36         | 0.36         | 0.36         |
| Days 7 and 8 (Study days 14 and 15)       | 0.36         | 0.36         | 0.72         |
| Days 9 and 10 (Study days 16 and 17)      | 0.36         | 0.72         | 0.72         |
| Days 11-40
(Study days 18-40)          | 0.72         | 0.72         | 0.72         |

Trained study personnel will evaluate heart rate, orthostatic blood pressure, pre-syncope and syncope signs and symptoms at all study visits during the titration period. If the study participant does not have bradycardia, orthostatic hypotension, or pre-syncope or syncope signs or symptoms as defined above, the dose of Lofexidine will be increased according to the titration schedule (**Table 2**). If bradycardia, orthostatic hypotension, or signs/symptoms of pre-syncope or syncope are identified at any point, the dose of Lofexidine will be lowered to the prior tolerated Lofexidine dose and the participant will remain at that dose for the duration of the study. At the beginning of the study, participants will be given a rescue pack of 36 tablets in case visits are missed. This will cover 3 days at the full dose.

The medical provider will inform the participant, verbally and with a take-home hand-out, of common side effects of lofexidine (dizziness, somnolence, dry mouth) and precautions to minimize risks associated with blood pressure (BP) decreases (hydration, standing up slowly). Participants will attend study visits three times a week during the induction period and throughout the study during which a UDS will be collected. The MUSC Investigational Drug Service will be responsible for randomization, will keep a record of the blind and will be available should unblinding be required. In the event that WorldMeds is unable to supply matching placebo. lofexidine tablets (supplied by US WorldMeds) will be encapsulated along with matching placebo capsules by Pitt Street Pharmacy, a specialty compounding pharmacy. Randomization will be stratified on presence/absence of other substance use as well as the presence/absence of significant childhood trauma (ACE>4).

e. Medication maintenance and adherence monitoring (Days 18-40). Trained study personnel will evaluate heart rate, orthostatic blood pressure, pre-syncope and syncope signs and symptoms once per week following the Lofexidine titration. If bradycardia, orthostatic hypotension, or signs/symptoms of pre-syncope or syncope are identified at any point, the dose of Lofexidine will be lowered to the prior tolerated Lofexidine dose and the participant will remain at that dose for the duration of the study. Participants will record themselves taking their medications A survey link will be sent to the participant's cell phone via app alert two to three times daily, depending on where they are in the medication schedule. Video capture will occur through the CREMA app. The research coordinator will review the subjects' videos before each study visit. As discussed, we have used this

technology successfully for medication adherence monitoring. To encourage compliance, participants will receive \$10 for each day that they complete their medication adherence videos.

- **f. Intervention phase** (Study Days 18-40). During the 5-week medication phase, study participants will come in three times per week for UDSs. Blood pressure and pulse will be assessed at each visit. If the SBP < 90 mmHg and > 20% below screening value and/or DBP is < 50 mmHg and > 20% below screening value, or the individual is complaining of symptoms of hypotension, the medication dosage will be reduced. If these symptoms do not resolve, the individual will be removed from the study and followed until vital signs normalize. EKG's will be performed at Weeks 4 and 6 to monitor QT intervals. A contingency-management procedure will be implemented to facilitate study visit adherence. The payments will start at \$4 and increase by \$4 for each consecutive visit.
- g. Virtual monitoring: In order to reduce face-to-face visits when necessary, remote monitoring may be done during the medication phase. At the randomization visit, patients will be given a wrist blood pressure cuff for at home monitoring, and they will be trained in testing orthostatic blood pressure. Patients will come to the clinic once a week for a UDS, to meet with staff/medical personnel and have ave orthostatic testing done, and receive medication refills. Two weekly visits will be conducted via Telehealth. Patients will be observed doing a saliva drug screen and doing orthostatic blood pressure testing. If patients are symptomatic or having difficulty with telehealth procedures, they may be asked to attend the clinic more frequently. Participants who are not comfortable with telehealth procedures may choose to attend clinic visits instead.
- C.2.c.5. Phase Two: Scripted Opioid Imagery and Laboratory Induction Session (Days 39 and 40). At the end of the five-week period of lofexidine or placebo administration, participants will return to complete a scripted opioid imagery taksk and a laboratory stress task (Trier Social Stress TSST). Tasks will Test, counterbalanced. Subjects will remain on study medications for the test days. Subjects who miss their scheduled visits may be re-scheduled for up to one week. a. Session Preparation. Participants will be instructed to arrive at 8:00am on the test days, and to avoid caffeinated beverages since caffeine can introduce variability in heart rate response. If the individual is nicotine-dependent, (s)he will be provided with a nicotine patch throughout their study visit. Upon arrival, the participant will be breathalyzed and

|            | TAB             | BLE 3: LAB TESTING TIMELINE                                |  |  |
|------------|-----------------|--|--|--|
|            | 8:15am          | UDS, Saliva  |  |  |
|            | 8:35 am         | Relaxation   |  |  |
| Test Day 1 | 8:55am          | Baseline 1 Subjective, physiologic, endocrine measurement  |  |  |
| st [       | 9:00am - 9:15am | TSST/Imagery   |  |  |
| Te         | 9:15am          | Subjective, physiologic, endocrine measurement             |  |  |
|            | 9:20am          | Subjective, physiologic, endocrine measurement             |  |  |
|            | 9:45am          | Subjective, physiologic, endocrine measurement             |  |  |
|            | 10:15am         | Subjective, physiologic, endocrine measurement             |  |  |
|            |                 |  |  |  |
|            | 815am           | UDS, Saliva  |  |  |
|            | 8:35am          | Relaxation   |  |  |
| Day 2      | 8:55am          | Baseline 1: Subjective, physiologic, endocrine measurement |  |  |
|            | 9:00am          | Opioid imagery/TSST  |  |  |
| Test       | 9:05am          | Subjective, physiologic, endocrine measurement             |  |  |
| _          | 9:10am          | Subjective, physiologic, endocrine measurement             |  |  |
|            | 9:35am          | Subjective, physiologic, endocrine measurement             |  |  |
|            | 10:05 am        | Subjective, physiologic, endocrine measurement             |  |  |

will provide a urine sample to be tested for drugs of abuse. For women, a pregnancy test will be done prior to the urine drug screen, and saliva will be collected for estrogen and progesterone measurement.

- **b.Progesterone and Estrogen.** As there is significant individual variability in progesterone and estrogen levels across the menstrual cycle, measurement of progesterone and estrogen at the time of testing in combination with the menstrual cycle history will allow us to approximate the menstrual cycle phase as well as to utilize all participants' data with absolute progesterone and estrogen levels as continuous measures.
- **c. Design timing.** Subjects will first undergo a progressive relaxation task. Baseline assessments of subjective, hormonal (cortisol), and physiologic measures (blood pressure and heart rate) will be collected following relaxation, 5 minutes before the stressor or imagery; TSST takes 15 minutes, and the imagery takes 5 minutes. At the end of the stressor of drug cue, a salivary sample will be collected to assay cortisol and physiological (blood pressure and heart rate) and subjective measures (Mood Rating Scale, Opioid Craving Questionnaire, STAI) will be obtained. Measurements will also be obtained at 5- 30-, and 60-minutes post-task.
- d. Trier Social Stress Task (TSST) is a standardized psychological stress challenge which has been used extensively in research studies. A meta-analysis supports its utility for evoking a HPA axis stress response in a laboratory setting (Dickerson & Kemeny, 2004). It has induced a robust and reliable physiological stress

response in cocaine, alcohol, and cannabis-dependent individuals in our previous studies (McRae et al., 2006; McRae-Clark et al., 2011; Waldrop et al., 2010). At test initiation, the participant is told that (s)he will give a speech and perform an arithmetic task. The topic of the speech will be why (s)he should be hired for a particular job (the individual's "dream job"). The participant will deliver the speech as though speaking to a group of potential employers. The experimenter then tells the participant that (s)he has 5 minutes to prepare the speech and starts the countdown clock (placed in view of the individual). The experimenter leaves the room and five minutes later, three individuals unfamiliar to the participant (the audience) enter the room; the individual is instructed by one audience member to stand and begin his/her prepared speech (without notes). The speech will be delivered for 5 minutes. If the individual pauses, (s)he will be instructed to continue. At the end of the speech task, the individual will be instructed to serially subtract 13 from 1,022 as quickly and accurately as possible. The mental math recitation will continue for 5 minutes, at the end of which time, the spokesperson will instruct the individual to stop and be seated, and the audience leaves the room.

- **e. Opioid imagery script.** We are using a scripted imagery paradigm developed by Sinha and Tuit (2012). A script will be developed based on staff interviews with subjects about a time they craved and used opioids. The 5-minute script will be audio-recorded and played back to the subject during the task. Subjects will be asked to listen and imagine the task as if they are there.
- **f. Assessments.** Self-Report Measures. Mood Rating Scale: As described above and used with the CREMA sessions, to allow for cross-task comparisons. State-Trait Inventory (STAI): The STAI is a 20-item self-report scale (Spielberger, 1983) employing a Likert-scale format with four responses per item (1-4). Ten of the STAI items measure feelings of stress and anxiety, while the remaining ten items measure feelings of relaxation. The STAI has good psychometric properties. Opioid craving will also be measured using a Likert scale format. We have had good success with this in prior studies in OUDs (Back et al., 2014) Physiological Measures. Heart rate and blood pressure will be measured using an intermittently inflatable cuff as indices of physiological arousal during the test session. Hormonal Measures. Cortisol: Cortisol will be measured in unstimulated passive saliva using the Salimetrics expanded range, high sensitivity salivary cortisol enzyme immunoassay kit. This kit has a lower sensitivity level of <0.003 μg/dL. The correlation between salivary and serum cortisol has been shown to be high (r=0.91, p<0.0001). Cortisol is commonly measured as an indication of stress response in human laboratory studies.

Modifications may be made to lab day procedures if necessary for patient and staff safety, ie fewer confederates, remote procedures.

- **g. Discharge.** Following assessments, participants will be given instructions to taper their lofexidine over the next five days. A member of the research staff will be available to discuss management of any craving or urges to use any substance if craving remains elevated at the end of study procedures.
- **C.2.c.6. Follow-up Assessment (Days 41-47).** During a one-week follow-up period, lofexidine will be tapered... They will come to the two times during the taper for BP monitoring (0.72 BID for two days, 0.36 mg BID for 2 days, 0.36 QD for 1 day). After five days, participants will return to the clinic and return clinic-provided phones, complete a questionnaire regarding their experience with the CREMA and REDCap surveys, and be provided referrals to treatment if interested.

Participant Compensation: Participants will be compensated \$40 for completing the screening visit, and an additional \$20 for completing the screening the first time they are scheduled. They will receive \$20 for the CREMA training and a \$25 bonus if they come to their first baseline visit as scheduled. They will receive \$10.00 for each day that all CREMA sessions are completed. During the opioid abstinence period, participants can earn a total of \$30 for completing drug testing (2 negative UDS compenstated at \$10 and \$20). During the medication period, subjects can receive up to \$10 for each day they complete medication videos and \$364 (\$4+\$8+\$12+\$16+\$20+\$24+\$28+\$32+\$36+\$40+\$44+\$48+ \$52) for completing study visits with UDS. Participants will be compensated \$10 for each blood pressure check during the tapering phase. Participants will also be compensated \$50 for completion of each human laboratory session, a \$50 bonus for completing both as scheduled, and \$100 for the follow-up. follow-up visit, for a total potential compensation of \$819 per participant plus earnings from CREMA and medication videos. Participants will be asked to complete a W-9. This document may be completed in person or via Doxy.me.

Confidentiality: Confidentiality of all research data will be maintained by keeping all data in a locked file, limiting access to the computer database to only study personnel, and by using patient code numbers as opposed to names on all paperwork.

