An EKG and physical exam including orthostatic hypotension testing will be conducted by a licensed medical provider. Serum will be collected for baseline labs and a UDS will be collected. If the participant is female, a pregnancy test will be done prior the urine drug screen. Females who are pregnant will not be allowed to participate. Participants at Shoreline will have labs drawn by Mako Medical Lab at the Shoreline site.

**C2.c4..** Remote screening visit:. Patients may also complete the initial visit remotely if warranted. In this case, subjects will be electronically consented using Doxy.me or RedCap or a combination. The informed consent will be emailed to the participant prior to the video call. The patient will have the opportunity to ask questions on the call and will electronically sign the document. A signed copy will be emailed to the participant. The M.I.N.I interview and medical history then be conducted, also via Doxy.me Patients will be advised to find a private location during these procedures to protect privacy and confidentiality. Patients will be sent survey links to complete self-report questionnaires. The blood draw, EKG and orthostatic BP will be done at Baseline. A physical exam may be done if it is warranted based on medical history. Urine drug screening and pregnancy testing will not be done until baseline for participants who screen remotely.

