#### **Exclusion Criteria**

- 1. Women who are pregnant, nursing or of childbearing potential and not practicing an effective means of birth control.
- 2. Evidence or history of major medical illnesses, including liver diseases, abnormal vaginal bleeding, suspected or known malignancy, thrombophlebitis, deep vein thrombosis, pulmonary embolus, clotting or bleeding disorders, heart disease, insulin-dependent diabetes, history of stroke or other medical conditions that the investigator deems as contraindicated for the individual to be in the study.
- 3. History of or current psychotic disorder or bipolar I affective disorder.
- 4. Current suicidal or homicidal ideation/risk.
- 5. Taking medications known to act on adrenergic systems (B-blockers; alpha agonists or antagonists)
- 6. Hypotensive individuals with a sitting blood pressure of < 90/50
- 7. QTc interval of >440 in males and > 460 in females as the combination of lofexidine plus methadone may increase the QTc interval. For males with a QTc of greater than >440, but less than 470 AND absence of any history of CV disease AND absence of family history of CV death, they are eligible for enrollment. For females with a QTc of greater than >460, but less than 490 AND absence of any history of CV disease AND absence of family history of CV death, they are eligible for enrollment.
- 8. Known allergy to lofexidine
- 9. Unable to comply with study procedures or pose threat to study staff.

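### The plan does not require the pre-dose heart-rate and orthostatic check to be passed before random assignment, so participants can be randomised, fail it and leave undosed

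*Combined protocol and SAP*

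**What the plan says.** Four places bear on the point.

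- **Trigger for assignment** (C.2.c.5, item d): "After two consecutive negative drugs screens have been obtained, participants will be randomly assigned to study medication". No heart-rate or blood-pressure condition is attached. Item b of the same section likewise makes two negative screens the gate into the medication phase.
- **The check** (same item): "Trained study personnel will evaluate heart rate, orthostatic blood pressure, and pre-syncope and syncope signs and symptoms prior to the initiation of Lofexidine". What it controls is dispensing: "Lofexidine will not be dispensed if the participant is found to have" clinically significant bradycardia, orthostatic hypotension, pre-syncope symptoms or syncope. The consequence of failing is: "Participants with bradycardia, orthostatic hypotension, pre-syncope or syncope would be terminated from the study".
- **Earlier testing.** For in-person screening, C.2.c3 says: "An EKG and physical exam including orthostatic hypotension testing will be conducted by a licensed medical provider". For remote screening, C2.c4 says: "The blood draw, EKG and orthostatic BP will be done at Baseline".
- **Listed exclusions** (C.2.c.2 and the Exclusion Criteria under Protection of Human Subjects). The only blood-pressure criterion is: "Hypotensive individuals with a sitting blood pressure of < 90/50". Neither an orthostatic drop nor bradycardia is listed.

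The Power and Sample Size paragraph in C.2.d counts 136 as randomised participants and expects 25% attrition from randomisation to the end of the five-week treatment period.

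**The concern.** A check that ends participation works as an eligibility check. If it is applied after allocation, those who fail are already randomised. They then have no medication-period data for any of the three aims:

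- no laboratory session on days 39 and 40 (Aim 1);
- no on-medication CREMA ratings (Aim 2);
- no relapse time, because that clock starts only after titration begins (Exploratory Aim 3).

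At most they leave baseline CREMA ratings, which the plan uses as a covariate.

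Two things are at stake. The first is precision, because each such person uses one of the 136 planned places. The second is clarity about who is analysed. The documents do not say whether a participant who is randomised but never dosed is analysed, excluded or replaced.

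**Working it through.** **1. Order of events.** Assignment depends on drug screens alone. The check depends on nothing but coming before the first dose. Item d does mention the randomization visit, but that phrase governs only the saliva samples from women; the sentence on the check names no visit. Two sequences therefore fit the text: screens, assignment, check, dose; or screens, check, assignment, dose. The text describes assignment first and calls failure a termination, not a screen failure, which points to the first sequence without stating it. Shoreline gives some support: the Investigational Drug Service both randomises and dispenses, and medication is delivered to staff at that site. If it is already there when the check is done, assignment came first. That is an inference.

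**2. Does earlier testing close the gap?** Orthostatic testing takes place before assignment on both screening routes. A positive result meets no listed exclusion, apart from the investigator's general discretion over contraindicating medical conditions. A person could therefore show an orthostatic drop at screening, be randomised, and be terminated for the same sign before dosing.

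**3. The plan's own sample-size figures.** Inputs from Power and Sample Size: d = 0.64, 80% power, 5% type 1 error (two-sided assumed), 39 per sex-by-treatment cell, total 156, 25% attrition, 136 randomised.

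- Per group for a simple two-group comparison: n = 2 × ((1.96 + 0.842) / 0.64)² = 38.3, rounded up to 39. This reproduces the 39.
- Completers expected from 136: 136 × 0.75 = 102, or 25.5 per cell.
- Randomised number needed for 156 completers: 156 / 0.75 = 208. The 136 is not reproduced. That is a separate and larger problem, and it neither supports nor weakens this point, but it means the plan has no slack.

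**4. Size of the loss.** The documents give no failure rate f, so f = 2%, 5% and 10% are assumptions.

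- Randomised and undosed: 136 × f.
- Completers if these losses are additional to the 25%: 136 × (1 − f) × 0.75.
- Randomised number needed to keep 102 completers in that case: 102 / (0.75 × (1 − f)), rounded up.
- Power with n per cell, on the plan's two-group basis: Φ(0.64 × √(n/2) − 1.96).
- Power with n per cell, as a true sex-by-treatment interaction (difference of differences): Φ(0.64 × √(n/4) − 1.96).

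| f | Undosed | Completers if additional | Per cell | Power, two-group | Power, interaction | Randomised to keep 102 |
|---|---|---|---|---|---|---|
| 0% | 0 | 102 | 25.5 | 62.8% | 36.5% | 136 |
| 2% | 2.7 | 100.0 | 25.0 | 61.9% | 35.9% | 139 |
| 5% | 6.8 | 96.9 | 24.2 | 60.5% | 35.0% | 144 |
| 10% | 13.6 | 91.8 | 23.0 | 58.2% | 33.5% | 152 |

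If the 25% already includes these people, planned completers stay at 102 for every f, and the completer and power columns keep their first-row values.

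**The case against.** The strongest reply is that the plan never says the check follows assignment. A site could do the check first and comply with every sentence. Orthostatic testing has also been done once already, and the investigator may exclude on medical grounds, so few people should fail for the first time on the dosing day. The 25% attrition runs from randomisation, which on its face covers anyone lost before dosing. The full analysis plan is said to sit in the Biostatistics Resource Core and may define the analysis set.

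Much of this stands. It limits the size of the problem and rules out three stronger readings that a reader might infer:

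- *That the check is definitely done after randomisation.* The order comes from the sequence of the text; only its position before the first dose is stated.
- *That the loss biases the treatment comparison or unbalances the arms through small stratified blocks.* The check precedes any study drug and is blinded, so failure should not depend on arm. The plan names two stratification factors but no blocks or block size.
- *That completers necessarily fall below 102.* This follows only if the losses come on top of the 25%.

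The reply does not remove the gap. No sentence makes a pass a condition of assignment, the earlier test has no listed consequence, and these documents do not say how a randomised, undosed participant is counted. If the intended order is check first, the same sentence is needed to say so.

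**Conclusion.** The point holds as a gap in the stated sequence: the plan allows participants to be randomised and then terminated before any dose. It is worth correcting, because the correction changes conduct and costs very little, but its effect is modest. Under an assumed failure rate of 2% to 10%, about 3 to 14 of the 136 would be affected. If those losses add to the 25% attrition, completers fall to about 100 to 92. Power then falls by about 1 to 5 percentage points on the plan's two-group basis (62.8% to between 61.9% and 58.2%), or about 1 to 3 points as an interaction (36.5% to between 35.9% and 33.5%). If the 25% already includes them, the planned completer count is unchanged and what remains is the avoidable use of randomised places and their undefined status in the analysis. The harm is to precision and clarity, not to validity.

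**What to change.** In C.2.c.5, item d, state that the heart-rate, orthostatic and pre-syncope evaluation is completed and passed before the Investigational Drug Service assigns treatment. Record those who do not pass as screen failures who do not count toward the 136. Leave the clinical criteria and their consequences as they are. Add one sentence to C.2.d on how anyone still randomised but never dosed, for whatever reason, is counted and analysed, and whether that person is replaced.

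The cost is a reordering of existing steps, with no added procedure. The one practical downside is at Shoreline, where medication is delivered to site staff: assignment and delivery may have to wait for the result of the check.

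### The titration plan has no rule to hold the dose until a safety check has been passed, and on a usual three-visit week one of the five increases can go unchecked

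*Combined protocol and SAP*

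**What the plan says.** Section C.2.c.5 (Phase 1), item d, says "lofexidine will be titrated over a 10-day period". Table 2 sets five two-day dose levels, with increases on titration days 3, 5, 7, 9 and 11. The first check, covering heart rate, orthostatic pressure and "pre-syncope and syncope signs and symptoms prior to the initiation of Lofexidine", is made before any drug is taken.

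After that, checks are made at study visits: "Participants will attend study visits three times a week during the induction period". If a check is clean, "the dose of Lofexidine will be increased according to the titration schedule". If it is not, the dose is "lowered to the prior tolerated Lofexidine dose and the participant will remain at that dose for the duration of the study". The virtual option in item g keeps three contacts a week, one in clinic and the rest remote: "Two weekly visits will be conducted via Telehealth".

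Missed visits are expected: "participants will be given a rescue pack of 36 tablets in case visits are missed". The text does not say whether the dose is held or raised when no check took place. Under Protections Against Risks, the provider may slow an individual's titration, but the stated trigger is hypotension or another troublesome side effect.

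**The concern.** The dose steps come faster than the visits: every 2 days, against an average of 7/3 = 2.33 days. The increase is conditional on a clean check, yet the schedule can reach an increase before any check on the current dose. Nothing in the text then stops the increase. The rescue pack supplies tablets, and the app prompts in item e follow the medication schedule. A missing check is not among the stated reasons to slow down.

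Two things are at stake. The visit check is the planned way to find bradycardia and orthostatic hypotension during titration. It also sets exposure, because a reduction lasts to the end of the study and so covers the laboratory sessions on study days 39 and 40. If the level below the current one was never checked, staff could take the prior tolerated dose to be that level or the last checked one.

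**Working it through.** **Inputs.** Table 2 daily totals are 0.36 mg (days 1–2), 0.72 (3–4), 1.08 (5–6), 1.44 (7–8), 1.80 (9–10) and 2.16 from day 11. There are three visits a week. The day-1 check precedes the first dose, which Table 2 places at bedtime.

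**The plan's own figure.** 5 levels × 2 days = 10 days, with full dose on day 11. This reproduces.

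**Average supply of checks.** 10 × 3/7 = 4.3 visits per 10 days, against 5 increases.

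**Counting rule.** A level counts as checked if a visit falls after its first day and no later than the day of the next increase, with the visit held before that day's new dose. The windows are days 2–3, 4–5, 6–7, 8–9 and 10–11.

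**Monday/Wednesday/Friday visits (assumed), day 1 a visit:**

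| Start | Visits to day 11 | Increase with no on-dose check | Next visit |
|---|---|---|---|
| Monday | 1, 3, 5, 8, 10 | day 7 (1.08 to 1.44 mg/day) | day 8 |
| Wednesday | 1, 3, 6, 8, 10 | day 5 (0.72 to 1.08) | day 6 |
| Friday | 1, 4, 6, 8, 11 | day 3 (0.36 to 0.72) | day 4 |

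Each start day has four on-drug visits. Removing any one leaves 2 of 5 increases unchecked, in all 3 × 4 = 12 cases. For example, a Monday start that misses day 8 goes from a check at 0.72 mg/day (day 5) to the next at 1.80 (day 10).

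**Sensitivity to what the protocol leaves open:**

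- Visits at midday, after the morning dose (Monday/Wednesday/Friday): 1 to 2 unchecked with full attendance, 2 to 3 with one missed.
- Any visit within the two calendar days of a level, counting the pre-drug day-1 visit: 0 (Monday or Wednesday start) or 1 (Friday start); 1 to 2 with one missed.
- Other fixed weekday patterns without three consecutive days, visit before the new dose: 1 to 2; 1 to 3 with one missed.
- Tuesday start with visits on days 1, 3, 4, 7, 9 and 11 (Tue, Thu, Fri, Mon, Wed, Fri), visit before the new dose: every window contains a visit, so 0; 1 with one missed.

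The range is therefore 0 to 2 with full attendance and 1 to 3 with one missed visit. Bunched visits fall outside it: Monday/Tuesday/Wednesday with a Wednesday start gives visits on days 1, 6, 7 and 8, which leaves days 3, 5 and 11 unchecked.

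**Ambiguity in the reduced dose.** Take an event found on day 8 after a Monday start. The previous Table 2 level is 1.08 mg/day (1.08/2.16 = 50% of target), and the last checked level is 0.72 (33%). The difference is 0.36 mg/day, or 17% of target.

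**The case against.** A reader might infer that three visits a week can never cover a two-day schedule. The documents do not support that. They fix no weekdays or visit times, and the Tuesday-start calendar above covers all five increases with three visits per calendar week. So would visits on days 2, 4, 6, 9 and 11 if the randomization visit were extra to the weekly three.

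A reader might also take the 13 escalating payments "for completing study visits with UDS" as confirming a Monday/Wednesday/Friday calendar. They do not. Over titration days 2–31 that calendar gives 13, 13 and 12 visits for Monday, Wednesday and Friday starts. Counting day 1 gives 14, 14 and 13. The total fits more than one arrangement.

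It can further be said that a clean visit simply means carry on with Table 2, and that no text requires a separate check for each step. That is a fair reading, and on it the protocol does not contradict itself. But it also lets the dose rise unchecked, most plainly after a missed visit.

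Other safeguards count too. An event found at any point triggers a reduction, participants are warned about side effects, and symptomatic participants on the virtual option can be brought in more often. With full attendance on the assumed calendar, the next visit is one day after the unchecked step. The dose ambiguity affects only participants whose event is found just after such a step, and the documents give no frequency for that. These points limit the size of the concern, but none supplies a hold rule.

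**Conclusion.** The point holds as a missing safety rule. Followed as written, the text can raise the dose with no check on the current level. The counts of one unchecked increase with full attendance and two after a missed visit rest on three assumptions: Monday/Wednesday/Friday visits, day 1 as one of them, and visits ahead of that day's new dose. Without these the supportable statement is the range of 0 to 2, and 1 to 3 with one missed visit. No spread-out schedule examined covers every step once a titration visit is missed, and that is the situation the rescue pack is meant for.

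This is a modest monitoring improvement and no reason to stop or redesign the trial. The Potential Risks section describes reported hypotension as generally mild.

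**What to change.** In item d of C.2.c.5 (Phase 1), add: *A Table 2 increase is taken only after a check (in person or telehealth) has been passed on the current dose. If a visit is missed, the participant stays on the current dose, using the rescue pack if needed, and resumes one step at a time at the next passed check. Prior tolerated dose means the highest dose at which a check was passed; if none was passed, the study physician decides between 0.36 mg/day and stopping.* Label the Table 2 days as earliest days, and carry the missed-visit rule into the hand-out and the app schedule.

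The cost is a short delay to full dose. On Monday/Wednesday/Friday visits, full dose is reached at the sixth visit: titration day 12 (Monday start) or 13 (Wednesday or Friday), instead of 11. One missed titration visit moves it to day 15 for all three start days. Since study day = titration day + 7, full-dose days before study day 39 fall from 39 − 18 = 21 to 39 − 19 = 20 or 39 − 20 = 19, and to 39 − 22 = 17 after one missed visit. No extra visits or tablets are needed.

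If the fixed days must stay, one telehealth check placed in the gap would cover the assumed calendar, at most 136 extra checks in all. The missed-visit rule would still be needed.
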